- 4. **Subject Population:** Provide a detailed description of the types of human subjects who will be recruited into this study.

Our study population will consist of adult subjects with ASD who have primary caregivers. Specifically, our population is individuals over the age of 18 participating, or with parents participating in local support and advocacy groups for ASD. Participants in this study will have prior, confirmed diagnoses of ASD in order to be considered for inclusion. In this pilot study we will include both higher functioning individuals with ASD (who will provide their own consent), as well as less cognitively able individuals (who will have consent provided by a guardian parent). All participants will be living with or closely engaged with a primary caregiver, and are expected to have at least moderate impairment related to social and communication deficits. Please see the study inclusion and exclusion criteria for a quantitative description of the study subjects.

5. **Inclusion/Exclusion Criteria:** What are the criteria used to determine subject inclusion or exclusion?

Inclusion criteria:

- Age: 18-60
- Gender: All
- Language: Communicative in English
- Participants with a prior diagnosis of DSM-5 ASD at some point in their lifetime OR a DSM-4 diagnosis of Autism OR a DSM-4 diagnosis of Asperger's syndrome OR a DSM-4 diagnosis of Pervasive Developmental Disorder Not Otherwise Specified.
- Symptoms of irritability, agitation or aggression as reported by parent and/or participant
- Aberrant behavior checklist Irritability Subscale (ABC-I) score of 16 or higher
- No changes in psychotropic medications within the past 14 days.
- Either lives with a primary caregiver or closely engaged with a primary caregiver who interacts with the patient daily
- BMI ≥ 17.5 and ≤ 45

Exclusion criteria:

• Age < 18 or > 60

- BMI < 17.5 or > 45
- Currently using tobacco or any nicotine products (transdermal, gum, e-cigarettes)
- · Changes in psychotropic medication management within the past 14 days
- Previous allergy to transdermal patches
- Patients with heart rate > 100 or < 50 or known history of cardiac rhythm abnormalities
- Systolic blood pressure > 150 or < 95; diastolic blood pressure > 90 or < 50
- No symptoms of irritability, agitation, or aggression as reported by parent and/or participant
- ABC-I score of less than 16
- No primary caregiver, or primary caregiver unable to assist with rating scales

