- 6. How will **eligibility** be determined, and by whom?

Eligibility will be determined by the investigators. Once potential participants or a parent makes contact telephonically, we will explain briefly some information about the study, and offer them the opportunity to present for a screening visit. We will explain that a diagnosis of ASD is required for participation in the study, and encourage participants or their parent to bring information about their prior diagnosis to the screening visit, but will not request any PHI over the phone. At the screening visit, we will again explain the study procedures, and determine whether participants meet inclusion and exclusion criteria. In order to confirm diagnosis, we will require potential participants to provide evidence of a prior diagnosis done by a psychiatrist or clinical psychologist.

7. **Risks:** Describe the reasonably foreseeable risks, including risks to subject privacy, discomforts, or inconveniences associated with subjects participating in the research.

The study has a number of risks:

•

Medication related: Side effects of transdermal nicotine exposure have been well studied, and participants may experience nausea, insomnia, headache, skin irritation, palpitations, and dizziness. These side effects were found to be dose related in healthy, non-smoking subjects, with 15 mg nicotine patch significantly less likely to cause side effects than higher dose such as 30 mg[47]. Specifically, in this study 8 non-smoking patients were given a 15 mg nicotine patch. Five of 8 patients experienced mild nausea and lightheadedness after one hour, while 3 of 8 did not have any side effects. Seven of 8 patients continued with the study. Studies of chronic transdermal nicotine in nonsmoking populations are very encouraging regarding tolerability. In a large study of transdermal nicotine for treating mild cognitive impairment in older adults, tolerability was excellent in the over 30 subjects randomized to nicotine treatment [48]. It is not known whether subjects with ASD will be more or less susceptible to the common side effects of transdermal nicotine, however, transdermal nicotine use has been reported in case series or trials of patients with advanced dementia and age, a population that is likely to be increasingly sensitive to nicotine than younger, healthier subjects[43, 44, 48-50].

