It should be noted that nicotine patches have been used successfully in populations with cardiovascular disease [54]. Although subjects with known cardiovascular disease, including hypertension, history of myocardial infarction, heart failure, or arrhythmia will be excluded, these data are reassuring given the possibility of enrolling a subject with a previously undiagnosed cardiovascular condition.

- **Inconvenience:** In order to be included in our study, participants should not be undergoing active changes in their psychotropic medications, reducing the likelihood that this may become a problem in the course of the study. We have limited the number of visits to three, which we believe to be the minimum number of visits yielding scientifically useful data.
- 9. Statistical Considerations: Describe the statistical analyses that support the study design.
- a) We plan to enroll approximately 16 subjects in this *pilot* study.

b) The major hypothesis of the study is that transdermal nicotine will *reduce* symptoms of aggression as quantified by the Aberrant Behavior Checklist (ABC) – irritability subscale. For comparison, risperidone in a large clinical trial (n=63) had a large effect size of d>1.0 as determined by an ABC-irritability subscale reduction from a mean baseline score of 26.6 to a score of 9.5 after 8 weeks of medication exposure[10]. To determine power estimates for our study, we used 26.6 as our mean estimate for the placebo group. Based on a literature review, we conservatively estimated a standard deviation of 10. We then calculated power for a range of effect sizes, estimating a correlation of 0.70 for repeated measures. Alpha was set at 0.05.The power estimates are displayed in Table 1.

 Table 1: Power estimates

Placebo Mean (SD)	Treatment Mean (SD)	Effect size (d)	Power
26.6(10)	22 (10)	0.59 (small- medium)	0.57
26.6(10)	20 (10)	0.85 (medium)	0.86
26.6(10)	15 (10)	1.27 (large)	0.99

These figures demonstrate our study is highly powered to detect medium and largesized differences between placebo and treatment groups.

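### Section 8 says known infarction, heart failure and hypertension are excluded, but the Section 5 list omits the first two and reaches hypertension only through measured blood pressure

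*Combined protocol and SAP*

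**What the plan says.** Two places in the combined protocol and SAP state who is excluded on cardiovascular grounds.

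Section 8 (Minimizing Risks), under Discomfort, first remarks that "nicotine patches have been used successfully in populations with cardiovascular disease". It then says: "Although subjects with known cardiovascular disease, including hypertension, history of myocardial infarction, heart failure, or arrhythmia will be excluded", and concludes that "these data are reassuring given the possibility of enrolling a subject with a previously undiagnosed cardiovascular condition".

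Section 5 (Inclusion/Exclusion Criteria) is introduced by the question "What are the criteria used to determine subject inclusion or exclusion". It has ten exclusion bullets, two of them cardiovascular:

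- The first deals with pulse and rhythm and excludes "Patients with heart rate > 100 or < 50 or known history of cardiac rhythm abnormalities".
- The second sets limits on the pressure reading taken at the visit: "Systolic blood pressure > 150 or < 95; diastolic blood pressure > 90 or < 50".

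Section 6 says "Eligibility will be determined by the investigators", at the screening visit and against the inclusion and exclusion criteria. The Visit 1 text in Section 3 likewise makes enrolment depend on those criteria.

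**The concern.** The two sections give different rules. Section 8 excludes by diagnosis or history. Section 5 excludes by rhythm history and by vital signs on the day. Staff who screen from the Section 5 list would have no prompt to turn away someone with a past infarction or heart failure whose heart rate and blood pressure are within limits.

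This matters because of how Section 8 argues. It offers the cited experience in cardiovascular patients as comfort about disease that nobody yet knew of. That argument presumes known disease has already been screened out, and the Section 5 list as written does not secure this.

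The protections that remain act only after exposure has begun. Withdrawal for chest pain or severe palpitations relies on the subject getting in touch with staff, and most or all of the nicotine week passes before the next scheduled visit.

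**Working it through.** No power or error-rate figure is involved. The check is a comparison of text, followed by a short count of days.

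**Step 1. Match each condition named in Section 8 to Section 5.**

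| Condition in Section 8 | Criterion in Section 5 | Result |
|---|---|---|
| Arrhythmia | History of rhythm abnormality, plus heart-rate limits | Covered |
| Hypertension | Measured pressure above 150 systolic or 90 diastolic | Covered by reading only, not by diagnosis |
| Myocardial infarction | None | Not covered |
| Heart failure | None | Not covered |

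The tally is 1 covered, 1 covered by measurement only and 2 not covered, out of 4. The exclusion list shows no redaction mark or sign of a lost item.

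**Step 2. Look for other text that closes the gap.** The Visit 1 description names rating scales and vital signs, with no medical history or ECG. Section 6 requires documentary evidence of one diagnosis only, ASD. The rhythm bullet implies a cardiac question, but only about rhythm. No other section repeats the infarction or heart-failure exclusion.

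**Step 3. Apply both rules to the same candidate.**

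- Known infarction or heart failure, heart rate 50 to 100, pressure within limits, no rhythm history: no Section 5 exclusion applies, but Section 8 excludes.
- Diagnosed hypertension controlled to 150/90 or below: no Section 5 exclusion applies. Section 8 excludes if the word *known* is read as referring to the diagnosis. That reading is arguable, not certain.

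**Step 4. Count nicotine days before the next scheduled visit.** The inputs are in Section 3: nicotine for the first 7 days in one sequence, nicotine for 7 days after 14 placebo days in the other, and visits at days 8 and 22. The text does not fix the day of the first patch, so both natural readings are shown.

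| First patch | Sequence | Nicotine days | Next visit | Nicotine days before it |
|---|---|---|---|---|
| Day 1 | Nicotine first | 1–7 | Day 8 | 7 of 7 |
| Day 1 | Placebo first | 15–21 | Day 22 | 7 of 7 |
| Day 2 | Nicotine first | 2–8 | Day 8 | 6 of 7 |
| Day 2 | Placebo first | 16–22 | Day 22 | 6 of 7 |

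Step 4 describes the schedule for every participant. It shows why the protection has to come at screening. It is not evidence of the mismatch, which rests on Steps 1 to 3.

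**The case against.** The strongest reply is that the exclusion already exists. Section 8 states it outright, it binds the investigators who decide eligibility, and Section 6 refers to inclusion and exclusion criteria without confining them to one section. On that view a candidate with a known infarction is ineligible under the protocol as a whole, and the list was simply not kept in step. This is fair as to intent, and it limits the claim to what could be missed. It does not make the sections agree: Section 5 is the part headed as the criteria, and an exclusion found only in a risk narrative is easily overlooked.

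The measured limits may be how the sponsor chose to define hypertension. That stands as a possible reading, so hypertension is a point to clarify, while infarction and heart failure are firm gaps.

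The absence of a medical history at Visit 1 is partly an argument from silence. Patch allergy, nicotine use and recent psychotropic changes are also criteria, so some history must be taken even though it is not itemised. This too is fair, but none of those items prompts a question about infarction or heart failure.

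The risk is also limited. The trial is a pilot of about 16 subjects aged 18 to 60, using 7 mg patches for 16 hours a day over 7 days. Each subject lives with a caregiver or is "closely engaged with a primary caregiver who interacts with the patient daily", and the protocol reports successful patch use in cardiovascular disease. All of this holds. It bears on how serious the point is, not on whether the two sections conflict.

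**Conclusion.** The concern holds. Sections 5 and 8 conflict on two conditions, infarction and heart failure, and arguably on a third, diagnosed hypertension that is controlled to within the measured limits. Arrhythmia is consistent between the two.

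The conclusion assumes that screening is done from the Section 5 list, as the wording of Sections 3 and 6 suggests. The hypertension part also depends on reading Section 8 as referring to a diagnosis.

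No number of affected subjects can be given, because the documents state no prevalence. They also quantify no harm. The point concerns eligibility and safety. It should be fixed, but it does not touch the power estimates or the planned analysis of the irritability score.

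**What to change.** Add one exclusion bullet to Section 5: known cardiovascular disease, meaning diagnosed hypertension, a history of myocardial infarction, or heart failure. Keep the existing rhythm, heart-rate and blood-pressure criteria. At the screening visit, ask the candidate and the caregiver about these diagnoses.

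If hypertension is meant to be defined by the measured limits alone, say so in Section 8 and leave it out of the new bullet.

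The cost is one line of text and one question at a visit that already takes place. Relative to the protocol as written, the added recruitment loss is zero, because the bullet excludes nobody whom Section 8 does not already exclude. Dose, visits, analysis and planned sample size do not change.

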 - a. Visit 1: As described above, informed consent will be obtained from participants or their legal guardian parent on meeting inclusion criteria and without exclusion criteria. Assent will be obtained from the participant in cases where informed consent is provided by a parent. Baseline behavioral rating scales will be performed. Specifically, we will obtain the Aberrant Behavior Checklist (ABC), State/Trait Anxiety Inventory (STAI), and Social Responsiveness Scale-Adults (SRS-A). These will be obtained from patients and primary caregivers as appropriate. Vital signs will be obtained. All participants will be given three weeks of identical appearing transdermal patches. Participants are randomized into two groups, one of which receives nicotine patches first and the other receives placebo patches first. Randomization will be performed by block randomization

using blocks of 4 subjects, and allocation concealment performed via the use of sequentially numbered, sealed opaque envelopes, on which the participant's identifying information is written prior to opening the envelope. In collaboration with the Investigational drug service at YNHH, we will link the allocation to a set of patches that are numbered in a simple fashion to help participants use the correct patch on the correct day. The first group will receive 7 days of nicotine patches, dose = 7 mg patches followed by 14 days of identically appearing placebo patches. The second group will receive 14 days of placebo patches, followed by 7 days of 7 mg nicotine patches. This design allows each participant to serve as his/her own control, with a seven-day washout period, which will eliminate carryover effects for those subjects receiving nicotine during the first 7 days of the study. Subjects will be asked to place the nicotine patch on their skin in the morning and remove the patch prior to sleep at night prior to sleep. This counter-balanced design is aimed to control for expectation bias and maximize validity. Duration of visit: 90 minutes.

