- b. Visit 2: Participants will return for a subsequent visit at day 8, at which point the above rating scale data will again be collected to measure both primary and secondary outcomes. Tolerability will be assessed as determined by vital signs, open-ended inquiry, and screening for common adverse effects of transdermal nicotine as observed in previous studies with non-smoking subjects. Open-ended inquiry for tolerability will be performed by asking subjects "What types of side effects or discomfort did you experience while wearing the patch during the preceding week?" and subject responses will be recorded by detailed notes. This approach may allow the investigators to gain a better understanding of the experience of the patch in individuals with ASD who might experience side effects differently than neurotypical individuals. Brief qualitative reports of the patient's subjective experience will be recorded by asking "In what ways did you find the patch helpful or harmful during the past week, if at all?". Detailed notes of responses will be written. Duration of visit: 60 minutes
- *c.* **Visit 3**: Participants will return for a third and final visit at day 22, at which point data will again be collected to measure primary and secondary outcomes, tolerability, and subjective experience (as detailed in Visit 2, above). *Duration of visit: 60 minutes*
- 4. Data analysis: Study results will be tabulated and subjected to statistical analysis to determine the presence of significant differences in primary and secondary outcomes between control and intervention. Statistical methods are outlined under 'statistical considerations' and performed by a trained statistician the YCCI and Yale Center for Analytical Sciences. Data regarding tolerability will be compared between control and interventions arms.

- 5. **Deviations from standard of care**: Current pharmacological standard of care for treatment of agitation and irritability in the population from which we are recruiting include mood stabilizers and antipsychotics[7, 9]. Patients currently taking these agents will not be required to discontinue this treatment, and the intervention is not expected to interfere with this treatment. Therefore, during the placebo period patients will not experience treatment below the standard of care, and during the active period they will continue to receive the standard of care, plus the active agent with its potential positive and negative effects.

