c) For the major hypothesis we will collect ABC rating scale data as well as at both baseline as well as at two other timepoints: after 7 days of transdermal nicotine treatment as well as after 7 days of placebo patch. Repeated measures analysis of variance (ANOVA) will be used with *treatment* (nicotine or placebo) as within-subjects factor and *order of treatment* (nicotine-placebo-placebo or placebo-placebo-nicotine) as a between-subjects factor. We will first test models with between and within subjects factors only. We will then test the interaction between *treatment* and *order*, in order to test whether treatment effects varied by administration order. McNemar's test or similar will be used for categorical variables such as whether or not a common, pre-defined side effect is reported. We will collect and report subjective experiences from patients and their caregivers but these will not be subjected to statistical analysis.

References

- 1. *American Psychiatric Association: Diagnostic and Statistical Manual of Mental Disorders*. 5 ed. 2013, Arlington, VA: American Psychiatric Association.
- 2. Kanne, S.M. and M.O. Mazurek, *Aggression in children and adolescents with ASD: prevalence and risk factors.* J Autism Dev Disord, 2011. **41**(7): p. 926-37.
- 3. Mandell, D.S., *Psychiatric hospitalization among children with autism spectrum disorders.* J Autism Dev Disord, 2008. **38**(6): p. 1059-65.
- 4. Higgins, D.J., S.R. Bailey, and J.C. Pearce, *Factors associated with functioning style and coping strategies of families with a child with an autism spectrum disorder.* Autism, 2005. **9**(2): p. 125-37.
- 5. Stith, S.M., et al., *Risk factors in child maltreatment: A meta-analytic review of the literature.* Aggression and Violent Behavior, 2009. **14**(1): p. 13-29.
- 6. Matson, J.L. and J. Jang, *Treating aggression in persons with autism spectrum disorders: A review.* Res Dev Disabil, 2014. **35**(12): p. 3386-3391.
- Politte, L.C., C.A. Henry, and C.J. McDougle, *Psychopharmacological* interventions in autism spectrum disorder. Harv Rev Psychiatry, 2014. 22(2): p. 76-92.
- 8. Brosnan, J. and O. Healy, *A review of behavioral interventions for the treatment of aggression in individuals with developmental disabilities.* Res Dev Disabil, 2011. **32**(2): p. 437-46.

- 9. Stigler, K.A. and C.J. McDougle, *Pharmacotherapy of irritability in pervasive developmental disorders.* Child Adolesc Psychiatr Clin N Am, 2008. **17**(4): p. 739-52, vii-viii.

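### Treatment-by-order is the period effect in this two-visit crossover, so it cannot by itself show that the drug effect depends on order, and the plan does not say which model gives the treatment test

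*Combined protocol and SAP*

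**What the plan says.** Section 3, Visit 1: "Participants are randomized into two groups, one of which receives nicotine patches first and the other receives placebo patches first". Allocation is by block randomization "using blocks of 4 subjects". One order has nicotine in the first week and placebo for the next two; the other has placebo for two weeks and nicotine in the third.

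Section 3, Visits 2 and 3: "Participants will return for a subsequent visit at day 8", and "Participants will return for a third and final visit at day 22". Each subject therefore has one nicotine and one placebo assessment, and order decides which comes at which visit.

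Section 9(c) plans a repeated measures ANOVA with treatment within subjects and order between subjects: "We will first test models with between and within subjects factors only". The treatment-by-order interaction is tested next, "in order to test whether treatment effects varied by administration order". There is no visit or period term. The data analysis paragraph of Section 3 says only that the aim is "to determine the presence of significant differences in primary and secondary outcomes between control and intervention". Neither place says which model answers the major hypothesis, or what follows if the interaction is significant.

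**The concern.** Two things are at issue.

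1. **Meaning of the interaction.** Section 9(c) reads it as a test of whether the drug works differently by order. It does compare the nicotine-placebo difference between orders, and it responds if that difference truly varies. But any change between day 8 and day 22 that both orders share goes into the same contrast. A plain time trend could be reported as order-dependent efficacy, or could cancel a real difference. The seven-day washout does not help, because no carryover is needed for this. The baseline ABC does not help either, because the planned treatment factor has only nicotine and placebo as levels.

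2. **Which model gives the treatment p-value.** The first model omits period. The second, once the interaction is added, is already the period-adjusted crossover analysis. The two can disagree on significance, and with unequal orders they also give different estimates.

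**Working it through.** **Inputs.** From Section 9(b): SD 10, correlation 0.70, alpha 0.05, and treatment means of 22 and 20 against 26.6 (differences of 4.6 and 6.6). Section 9(a): "We plan to enroll approximately 16 subjects", taken as 8 per order. Assumed here, because the protocol gives no figure: two-sided testing, the size of the Visit 2 to Visit 3 shift π (defined as the change under placebo), and the completer splits.

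SD of a within-subject difference = 10 × √(2 × 0.30) = 7.75.

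**The protocol's own figure.** A two-sided paired t-test at n = 16 gives power 0.60, 0.89 and above 0.99, against 0.57, 0.86 and 0.99 in Table 1. n = 15 gives 0.57, 0.87 and above 0.99. The third effect size, 11.6/7.75 = 1.50, does not match the stated 1.27. This is a separate matter and does not affect what follows.

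**The identity.** In ±1 coding:

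| Order | Visit | Treatment | Order code | Treatment × order | Period |
|---|---|---|---|---|---|
| Nicotine first | day 8 | +1 | +1 | +1 | +1 |
| Nicotine first | day 22 | −1 | +1 | −1 | −1 |
| Placebo first | day 8 | −1 | −1 | +1 | +1 |
| Placebo first | day 22 | +1 | −1 | −1 | −1 |

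The last two columns are identical. Likewise treatment × period equals order. Intercept, treatment, order and period use up all four cell means, so nothing is left for a separate carryover or treatment-by-period term.

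**Interaction test.** Let the nicotine effect be τ₁ in the nicotine-first order and τ₂ in the other. Nicotine minus placebo is τ₁ − π in the first order and τ₂ + π in the second. The contrast is τ₁ − τ₂ − 2π: one number for two unknowns. Its standard error at 8/8 is 7.75 × √(1/8 + 1/8) = 3.87, on 14 degrees of freedom.

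- Constant effect (τ₁ = τ₂), noncentrality 2π/3.87: significant in 7.7%, 16.1%, 30.3%, 48.5% and 82.1% of trials at π = 1, 2, 3, 4 and 6.
- True 6.6-point difference between orders: 35.5% with no shift. A 3.3-point shift in the opposing direction gives 6.6 − 2 × 3.3 = 0, hence 5.0%. In the reinforcing direction the contrast is 13.2 and the rate 88.6%.

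**Treatment test at 8/8.** Both models give the same estimate. Without period, the shift stays in the error: the expected variance of the differences is 60 + 16π²/15. At π = 4 this is 77.1, so the SD is 8.78 instead of 7.75. Simulation (400,000 trials per setting) gives:

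| Shift | Power 4.6, no period | Power 6.6, no period | Models disagree on significance (4.6) |
|---|---|---|---|
| 1 | 0.60 | 0.89 | 3% |
| 2 | 0.58 | 0.87 | 4% |
| 3 | 0.54 | 0.86 | 7% |
| 4 | 0.50 | 0.83 | 11% |
| 6 | 0.39 | 0.74 | 21% |

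With period, power is 0.60 and 0.89 at every shift. With no shift the models still disagree in 3% of trials.

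**Unequal completers.** The first model's bias is π × (difference in completers)/(total). At π = 4 this is 4 × 1/15 = 0.27 at 8/7, 4 × 2/14 = 0.57 at 8/6 and 4 × 4/14 = 1.14 at 9/5. It favours nicotine if the nicotine-first order is larger and scores worsen, or if the placebo-first order is larger and scores improve; otherwise it works against nicotine.

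| Completers | Power 6.6, favourable / unfavourable | With period | False superiority, favourable / unfavourable |
|---|---|---|---|
| 8/7 | 0.83 / 0.76 | 0.86 | 1.9% / 1.0% |
| 8/6 | 0.83 / 0.68 | 0.825 | 2.7% / 0.7% |
| 9/5 | 0.89 / 0.59 | 0.80 | 4.7% / 0.4% |

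False superiority means nicotine declared better when it has no effect (nominal 2.5%). Total two-sided error at 9/5 is 5.1%, so the inflation is in one direction only.

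**The case against.** The strongest reply is that little goes wrong at the planned size.

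- **At 8/8 the estimate is the same and the first model is only conservative.** This stands. The power loss is about 0.02 or less at shifts of 1 to 2, and model disagreement there (3% and 4%) barely exceeds the 3% seen with no shift. The large figures need a shift of about 6 points, close to the 6.6-point drug effect in Table 1, and no document supports any particular shift.
- **9/5 cannot come from exactly 16 enrolled.** True: it needs slight over-enrolment and one-sided losses, which a target of about 16 allows. From exactly 16, at a 4-point shift in the favourable direction, false superiority is 3.7% at 8/5 and about 5.2% at 8/4, so inflation can still arise. It is uncommon. With independent dropout at an assumed 10%, completers differ by 3 or more in 3.7% of trials and by 4 or more in 0.5%; at an assumed 20%, in 11% and 2.7%. Smaller gaps are easily reached: Sections 7 and 8 provide for withdrawals, and stopping at 14 enrolled gives 8/6 in one trial in three (2 of the 6 possible blocks of 4 begin with the same order twice).
- **The interaction does compare the drug difference between orders, and the plan attaches no decision to it.** The first half is correct. But Section 9(c) states what the test is for, and a significant result cannot carry that meaning on its own.
- **The period-adjusted model is already planned.** It is, as the second step. Nothing says that it gives the treatment test, and the word order suggests the first model as easily.
- **This is a pilot.** Efficacy is nonetheless a stated aim in Section 1, and Section 9(b) names a major hypothesis and claims power for it.

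**Conclusion.** The concern holds and should be fixed. That treatment-by-order equals period is exact and needs no assumption. The stated reading of the interaction is therefore unsupported as written, and the model for the main test is not named.

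The practical size depends on a shift that the documents do not give. At 8/8, false signals of order dependence run from 8% at a 1-point shift to 82% at 6 points, and the harm to the treatment test is lost power only. Bias appears only with unequal completers, in either direction. It raises false claims of superiority materially only when the imbalance is marked; at 8/6 the rate never exceeded 2.9% at the shifts tried, up to 6 points. All figures rest on the protocol's SD and correlation and on two-sided 5% testing.

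**What to change.** In Section 9(c), name one primary model: ABC irritability at Visits 2 and 3, with treatment, period and order as fixed effects and subject as random. Equivalently, keep treatment-by-order in the ANOVA whatever its p-value and label it period. Take the treatment estimate, confidence interval and p-value from that model. Replace the interaction sentence with wording such as:

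> In this design the treatment-by-order term is aliased with period. It is kept in the model as the period effect and will not by itself be interpreted as showing that the treatment effect differs by order. Carryover and treatment-by-period effects cannot be separated from the order and period terms. The order main effect is a low-power check only and does not change the primary analysis.

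No new data, visits or subjects are needed. At 8/8 the cost is one residual degree of freedom (15 to 14): with no shift, power goes from 0.603 to 0.599 for 4.6 points and from 0.889 to 0.886 for 6.6. If orders end unequal and there is no shift, the cost is larger: 0.539 to 0.525 and 0.838 to 0.825 at 8/6, and 0.539 to 0.499 and 0.838 to 0.801 at 9/5.

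### Side effects are compared only as reported yes/no, with no severity grade and no pre-patch screen, so the planned paired test cannot register worsening of a symptom reported in both weeks

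*Combined protocol and SAP*

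**What the plan says.** Tolerability is one of the aims in section 1 of the combined protocol and SAP.

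- **Visit 1 (section 3, Study design, a).** The baseline scales are listed: "Specifically, we will obtain the Aberrant Behavior Checklist (ABC), State/Trait Anxiety Inventory (STAI), and Social Responsiveness Scale-Adults (SRS-A"). For safety, "Vital signs will be obtained". No symptom checklist before the first patch is mentioned.
- **Visit 2, day 8 (section 3, Study design, b).** "Tolerability will be assessed as determined by vital signs, open-ended inquiry, and screening for common adverse effects of transdermal nicotine". The open-ended question is "What types of side effects or discomfort did you experience while wearing the patch during the preceding week", with answers kept as notes.
- **Visit 3, day 22 (section 3, Study design, c).** The Visit 2 assessments are repeated.
- **Expected effects (section 7, Medication related).** "participants may experience nausea, insomnia, headache, skin irritation, palpitations, and dizziness".
- **Analysis (section 9, item c).** McNemar's test or similar is named for categorical variables such as "whether or not a common, pre-defined side effect is reported". Subjective experiences are reported but not analysed statistically. Section 3, item 4, says that tolerability will be compared between treatments but gives no method.

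None of these places defines a severity grade, a change from baseline or a treatment-emergent event.

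**The concern.** The efficacy scales and vital signs have a pre-patch value; the side-effect symptoms do not. Most of the listed symptoms are non-specific and can be present in someone who has never worn a patch. Participants may also stay on mood stabilisers and antipsychotics (section 3, item 5).

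A participant with a persisting symptom who reports it at both visits is a yes/yes pair. McNemar's test uses only discordant pairs, so this participant contributes nothing, whether the symptom was unchanged or went from mild to severe on nicotine. The same symptom is counted in the rate of each week.

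With about 16 participants, few pairs can be spared. The stake is the sensitivity of the only named test of a stated aim, and the meaning of the side-effect rates that a later trial would draw on.

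**Working it through.** The plan gives no figure for the side-effect analysis, so there is none to reproduce.

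**Inputs from the documents**
- About 16 participants, each receiving both treatments (section 9, item a; section 3, Visit 1).
- Alpha 0.05 (section 9, item b, stated for the efficacy power); two-sided is assumed.

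**Inputs assumed**
- Number with the symptom before any patch: 0, 3 or 5 of 16 (0%, 19%, 31%). Each is taken to report it in both weeks.
- Probability of a new or worsened symptom, p_N on nicotine and p_P on placebo: four pairs of values, shown below. The only related figure in section 7 is 5 of 8 = 62.5%, from a 15 mg patch in a cited study; this trial uses 7 mg, and section 7 calls the effects dose related.
- The two weeks are independent within a participant. Worsening in those already affected is as frequent as new onset in the others.

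**Step 1: pairs needed.** The exact two-sided p-value when all m discordant pairs point one way is 2 × 0.5^m. For m = 5 it is 0.0625; for m = 6 it is 0.031. At least six discordant pairs are therefore required.

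**Step 2: discordant probabilities.** Among participants who can change category:
- yes on nicotine only: p_N × (1 − p_P)
- yes on placebo only: (1 − p_N) × p_P

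At 50% vs 5% these are 0.50 × 0.95 = 0.475 and 0.50 × 0.05 = 0.025, a total of 0.50. The expected number of discordant pairs is 16 × 0.50 = 8.0 if all pairs are informative, 13 × 0.50 = 6.5 if 3 are lost, and 11 × 0.50 = 5.5 if 5 are lost.

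**Step 3: power.** Exact paired binomial test, summed over all possible outcomes:

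| p_N vs p_P | 0 affected (16 pairs) | 3 affected (13 pairs) | 5 affected (11 pairs) |
|---|---|---|---|
| 62.5% vs 10% | 0.81 | 0.66 | 0.51 |
| 50% vs 5% | 0.71 | 0.53 | 0.36 |
| 50% vs 10% | 0.54 | 0.38 | 0.26 |
| 25% vs 5% | 0.10 | 0.05 | 0.02 |

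Under the equal-frequency assumption, the 16-pair column is also the power when worsening is counted for everyone. Reading across a row gives the loss from yes/no coding.

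**Step 4: weekly rates.** With a share q already affected, the yes/no rate is q + (1 − q) × p. For q = 5/16 = 0.3125:
- nicotine: 0.3125 + 0.6875 × 0.50 = 65.6%, against 50% new or worse (+15.6 points)
- placebo: 0.3125 + 0.6875 × 0.05 = 34.7%, against 5% (+29.7 points)

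The visible difference is 65.6 − 34.7 = 30.9 points instead of 45.

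**Step 5: which change recovers the loss.** A Visit 1 yes/no screen alone recodes yes/yes as no/no. Both are concordant, so McNemar's test is unchanged. A severity grade at Visits 2 and 3 turns a pair that is worse on nicotine into a non-tied pair for a sign or signed-rank test. The Visit 1 value is needed for the weekly rates in step 4.

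**The case against.** Much of the opposing case stands.

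- **The crossover supplies a control.** Each participant also has a placebo week, so a steady pre-existing symptom creates no false difference. A reader might infer that the missing baseline biases the comparison; it does not.
- **Worsening may show elsewhere.** A reader might infer that it cannot appear at all. Detailed notes are taken at both visits, vital signs have a Visit 1 value, and under section 8 (Discomfort) patch removal and withdrawal depend on severity in both treatments. However, no severity analysis of any of these is planned. The words allowing a similar test in section 9, item c, leave room but commit to nothing.
- **The form is not shown.** What is analysed is a reported side effect, and the open-ended question asks about the time on the patch. Someone with chronic headache might not report it. A yes in both weeks is therefore a condition of the point, not a certainty.
- **Not every item is exposed.** Skin irritation at the patch site cannot predate the patch.
- **Background drugs are weak evidence.** Section 2 does call their side effects significant, but it means metabolic effects in particular. It does not show that headache, nausea or insomnia is common beforehand.
- **A test in 16 people is weak anyway.** At 25% vs 5%, power is only 0.10 with all pairs informative. This limits what any coding can achieve; it does not justify discarding severity where event rates are higher.

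**Conclusion.** The point holds as a loss of sensitivity in the planned yes/no test, together with inflated weekly rates. It applies to non-specific symptoms that predate the patch and are reported in both weeks.

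The size rests wholly on assumed prevalence and event rates. Across the four scenarios, having 5 of 16 affected lowers power from 0.81 to 0.51 at the most favourable rates and from 0.10 to 0.02 at the least. It would also be wrong to say that both weekly rates rise by the full pre-existing 31%. Compared with a new-or-worse count at 50% vs 5%, the rise is about 16 points on nicotine and 30 on placebo.

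The planned analysis is valid but less informative than it could be at little cost. The change should be made before enrolment, because a pre-patch value cannot be collected later.

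**What to change.** 1. On the existing checklist, score each item none/mild/moderate/severe at Visits 2 and 3. In section 9, item c, add a paired comparison of the severity scores between the nicotine and placebo weeks (sign or signed-rank test), reported beside the yes/no count. This step recovers the lost sensitivity.
2. Run the same checklist at Visit 1, before the first patch, and state that weekly side-effect rates count only symptoms that are new or more severe than at Visit 1. Patch-site items need no baseline.

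The cost is one four-level column on the form and a few minutes of added interview burden, within a Visit 1 already planned at 90 minutes. No extra visit, staff or change in clinical handling is involved.
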